| Intervention | 
The intervention will include 5 activities, each supported by a specific electronic tool:
 
A) Acutely ill children will be assessed, diagnosed and treated by routine clinicians guided by the ePOCT+ application loaded on a tablet or PC.
 
The intervention will be undertaken in routine PHC facilities in Tanzania and entails the implementation of the ePOCT+ tool for patient assessment and management, with provision of associated POC tests. Healthcare providers will use ePOCT+ throughout their medical consultations for children aged 0-14 years presenting with an acute medical or surgical problem. The tool will not be used for managing emergency cases. These cases will be identified by the tool in the beginning of the consultation (triage stage) and referred immediately to a higher level health facility. The CDSA of ePOCT+ is based on applicable Tanzanian national and international guidelines for pediatric clinical management (TZ version of IMNCI 2014; WHO Pocket Book of Hospital Care for Children 2013; TZ National Guidelines for the Diagnosis and Treatment of Malaria 2014; TZ Standard Treatment Guidelines and Essential Medicines list for Children and Adolescents 2018; Standard Treatment Guidelines & National Essential Medicines List Tanzania Mainland 2017 (Adults); TZ National Guideline for Neonatal care and Establishment of Neonatal Care Unit 2019; TZ National Guidelines for the Management of Tuberculosis in Children 2016; WHO IMAI guidelines 2009). Before implementation, the medical algorithm will be reviewed by Tanzanian key experts in child health (Pediatric Association of Tanzania; Ministry of Health; Muhimbili National Hospital). Most of the algorithm content was previously validated in Tanzania (see background section). Specifically, the tool will guide clinicians on:
 
 i) Decision on immediate referral to hospital versus home-based treatment ii) Medical history (questions to ask caregivers and/or children) iii) Physical exam (signs to look for) iv) POC diagnostic tests (which should be performed in a given clinical context) v) Diagnoses vi) Treatments (including medicines and supportive treatments) vii) Counseling (explanation on final diagnoses, treatments, and follow-up) 
B) The algorithm will be regularly updated according to trends in the collected data. The modifications will be designed by clinical experts based on the clinical and microbiological surveillance data collected during the study. Approved changes will then be integrated into the algorithm using the MedAL-Creator tool that allows physicians without any IT/programming skills to modify the decision tree.
 
During Phase 2, the modifications designed by the clinical expert group will be tested on retrospective data before being introduced in the electronic application. Each modification will then be loaded on the tablets or PCs of the relevant HCWs (for example of a certain region where an epidemic is occurring) with a message explaining the rationale and evidence behind this change in the algorithm.
 
C) HCWs will be trained through an initial in-person session and an e-learning platform available online (Phases 1 and 2)
 
Initial centralized training on essential clinical skills, the evidence and guidelines behind the content of the algorithm, the rational use of antibiotics and the practicalities around the use of the electronic tool will be provided to clinicians working in
 |

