| Outcomes | 
Objective 1 (Improve integrated management of children with an acute illness):
 
Co-Primary outcome measures (cluster randomized controlled study in Phase 1):
 
 (i) % of children cured at day 7* in the intervention group (ePOCT+) as compared to control group (routine care) (ii) % of children prescribed an antibiotic at initial consultation, as reported by HCW_s, in the intervention group (ePOCT+) as compared to control group (routine care) 
* according to caregivers contacted through phone or home visit (non-referred secondary hospitalizations will however be considered as clinical failures even if the child is already cured at day 7)
 
Primary outcome indicators (monitored over time and across geographical areas in all HF_s in Phase 2):
 
 - % of children prescribed an antibiotic at initial consultation - % of children cured at day 7 
Secondary outcome measures (compared between intervention and control HF_s in Phase 1) or indicators (monitored over time and across geographical areas in all HF_s in Phase 2):
 
Re-attendance visits:
 
 - % of children with ≥ 1 unscheduled re-attendance visits at any HF by day 7 
Severe clinical outcome by day 7:
 
 - % of children with non-referred secondary hospitalization by day 7 - % of children who have died by day 7 
Primary referrals:
 
 - % of children referred to hospital or admitted to inpatient ward at a health centre at initial consultation - % of children who were hospitalized among those referred (i.e. referral completed) 
Appropriate case management for malaria at initial consultation
 
 - % of febrile children tested for malaria - % of malaria positive children prescribed an antimalarial - % of malaria negative children prescribed an antimalarial - % of untested children prescribed an antimalarial 
Appropriate case management for other conditions at initial consultation
 
 - % of key symptoms and signs checked and diagnostic tests performed by HCW_s - Distribution of final diagnoses (including their severity) made by HCW_s - Concordance between treatment prescribed and final diagnoses made by HCW_s |

| | |
|--|--|

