These measures or indicators include the evaluation of the effects of the use of ePOCT+ (versus routine care in Phase 1; over time and across geographical areas in Phase 2) for managing sick children aged under 15 years presenting to PHC facilities on:

Unscheduled secondary consultations:

- % of children with one or more unscheduled re-attendance visits at any HF by day 7

Severe outcome by day 7:

- % of children with non-referred secondary hospitalization by day 7
- % of children who have died by day 7

Primary referrals:

- % of children referred to hospital or admitted to inpatient ward at a health centre at initial consultation
- % of children who were hospitalized among those referred (i.e. referral completed)

Appropriate case management for malaria at initial consultation

- % of febrile children tested for malaria
- % of malaria positive children prescribed an antimalarial
- % of malaria negative children prescribed an antimalarial
- % of untested children prescribed an antimalarial

Appropriate case management for other conditions at initial consultation

- % of key symptoms and signs checked and diagnostic tests performed by HCWs
- Distribution of final diagnoses (including their severity) made by HCWs
- Concordance between treatment prescribed and final diagnoses made by HCWs
- Concordance between final diagnoses as proposed by ePOCT+ and final diagnoses by HCW (*intervention HFs only*)

Definitions used for the outcome measures and indicators of objective 1

- Clinical cure is a positive answer to the question “Is the child cured?” OR “Has the child improved?” (if not cured) asked to caregiver through a phone call (or home visit) at day 7. Non-referred secondary hospitalizations (see definition below) will however be considered as clinical failures even if the child is already cured at day 7.
- Initial consultation is the first visit of a sick child for an acute problem at a HF participating in the study (and thus registered electronically); timeframe from completion of the initial visit up to midnight of the same day.
- Re-attendance visit is a consultation (not necessarily at a HF participating in the study) taking place from the day after initial consultation up to day 7 included. A re-attendance visit can be scheduled (proposed by the HCW on a certain day) or unscheduled (upon decision by caregivers).

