Analyses will follow CONSORT guidelines (Schulz et al. 2010, Piaggio et al. 2012) and intention-to-treat (ITT) principles, that is including all participants as randomized. A flowchart will describe the inclusion and follow-up of participants by study arm. Baseline characteristics will be described by study arm with summary statistics such as median and interquartile range or number and percentage; no formal testing between arms will be performed (Pocock et al. 2002). Outcomes will be described by arm using summary statistics. For the non-inferiority comparison between ePOCT+ and the control arm for clinical cure, a CI approach will be used. A figure illustrating the CIs and the non-inferiority margin will be presented. Primary analyses for the non-inferiority comparison will be performed on both the per protocol and ITT sets (Committee for Proprietary Medicinal P 2001). If ePOCT+ is found to be non-inferior to the control in terms of clinical cure rate, then we will assess for superiority using the ITT set. If non-inferiority is established, we will test for significant differences in the co-primary outcome of antibiotic prescription rate. For this outcome, the percentage of patients receiving antibiotics at day 0 will be assessed using multi-level logistic regression model regression with the cluster included as a random effect. Binary secondary outcomes will be evaluated in the same way. All estimates will be reported with 95% confidence intervals (CI).

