6.1.3. Exploratory outcomes

All exploratory outcomes are compared between the intervention (medAL-mentor) and control (routine care) arms.

a. Antibiotic prescription over time (longitudinal analysis)

Outcome measure: number of children for whom at least one systemic (oral or parenteral) antibiotic has been prescribed during consultation, over all eligible children, every week of the study period, as reported by the HCWs in the routine registry

Timing and method of assessment: documented by the HCW at the end of the consultation (routine registry) at day 0

b. Antibiotic prescription in children managed with and without ePOCT+

Outcome measure: number of children for whom at least one systemic (oral or parenteral) antibiotic has been prescribed during consultation, over all eligible children, as reported by the HCWs in the routine registry for children managed with and without ePOCT+

Timing and method of assessment: documented by the HCW at the end of the consultation (routine registry) at day 0

c. Antibiotic prescription reported in ePOCT+ versus in routine data (data consistency)

Outcome measure: number of children for whom at least one systemic (oral or parenteral) antibiotic has been prescribed during consultation systemic as reported by the HCW in ePOCT+ over number of children for whom at least one systemic (oral or parenteral) antibiotic has been prescribed during consultation systemic as reported by the HCW in the routine registry

Timing and method of assessment: documented by the HCW during the consultation (medAL-reader) and at the end of the consultation (routine registry) at day 0

d. Completion of ePOCT+

Outcome measure: number of consultations completed with ePOCT+, over all consultations started with ePOCT+

Timing and method of assessment: documented by the HCW during the consultation (medAL-reader) at day 0

e. Appropriate case management for malaria

Outcomes measure:

- % of consultations with febrile children tested for malaria
- % of consultations with children with a positive malaria test prescribed an antimalarial
- % of consultations with children with a negative malaria test prescribed an antimalarial
- % of consultations with untested children prescribed an antimalarial

Timing and method of assessment: documented by the HCW during the consultation (medAL-reader) at day 0

f. Appropriate case management for acute respiratory infections

Outcomes measure:

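### The antimalarial outcomes compare Phase 1 arms only within malaria test-status groups, and ePOCT+ can change who falls into those groups

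*Protocol*

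**What the plan says.** Protocol 7.1 lists four outcomes for malaria case management at the initial consultation. One is the percentage "of febrile children tested for malaria". The other three are antimalarial prescribing among malaria-positive children, the percentage "of malaria negative children prescribed an antimalarial", and the percentage "of untested children prescribed an antimalarial". The synopsis describes the group as "Secondary outcome measures (compared between intervention and control HF_s in Phase 1", and 7.1 introduces it as evaluating effects of ePOCT+ against routine care.

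Under 7.1's definitions, malaria testing is an order placed by the health worker during the visit. Directing tests is part of the intervention: the synopsis says that the tool guides clinicians on "POC diagnostic tests (which should be performed in a given clinical context". Table 2 targets the malaria rapid test at patients with fever, and 8.2 describes the unmodified fever branch as recommending a test for every febrile child.

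Section 10.3 states "intention-to-treat (ITT) principles, that is including all participants as randomized". It applies a multilevel logistic model to antibiotic prescription and adds: "Binary secondary outcomes will be evaluated in the same way". It does not discuss denominators that the intervention can alter. No listed antimalarial outcome uses all enrolled children, or all febrile children, as its denominator.

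The supplied SAP, for the medAL-mentor ancillary study, repeats the four outcomes as exploratory in 6.1.3, including the percentage "of consultations with untested children prescribed an antimalarial".

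**The concern.** Randomisation makes the enrolled children in the two arms comparable, apart from differences in who attends and consents. It does not make the untested children, or the test-negative children, comparable. Those groups form at the consultation, and the intervention helps to form them. A child who is untested under routine care may be tested and negative under ePOCT+. If that child's chance of an antimalarial differs from that of the group left or the group joined, both percentages change although clinicians follow the same prescribing rules as before.

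Hypothesis 1.1 claims more rational antimicrobial prescribing, and the synopsis counts antimalarials within that term. These outcomes are the antimalarial evidence for it. As listed, they mix two effects: how many and which children are tested, and what is prescribed once the result, or its absence, is known. A reader could take a change in group composition for a change in prescribing, in either direction.

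**Working it through.** The documents state no rate, effect or power for these outcomes, so there is no plan figure to reproduce. The check asks whether the percentages can move when prescribing rules are identical in both arms and only testing differs. All rates below are assumptions.

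**Model.** There are three child types: afebrile, febrile with low suspicion of malaria, febrile with high suspicion. For type k, w is the share of children, t the probability of being tested, q test positivity, u the probability of an antimalarial if untested, and n the same if negative.

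- Negatives treated = Σ w·t·(1−q)·n / Σ w·t·(1−q)
- Untested treated = Σ w·(1−t)·u / Σ w·(1−t)
- Treated without a positive test, over all children = Σ w·(1−t)·u + Σ w·t·(1−q)·n

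**Inputs, same in both arms:** w = 40/40/20%; q = 1/4/12%; u = 1/10/50%; n = 1/3/15%.

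**Reference arm:** t = 15/50/80%.

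- Negatives: (0.0594×0.01 + 0.1920×0.03 + 0.1408×0.15) / 0.3922 = 0.0275/0.3922 = 7.01%
- Untested: (0.34×0.01 + 0.20×0.10 + 0.04×0.50) / 0.58 = 0.0434/0.58 = 7.48%
- All children: 0.0434 + 0.0275 = 7.09%

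**Changing only testing:**

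| Testing (afebrile/low/high) | Negatives treated | Untested treated | Treated without a positive test, all children |
|---|---|---|---|
| Reference 15/50/80% | 7.01% | 7.48% | 7.09% |
| Febrile testing up: 15/90/95% | 0.0360/0.5722 = 6.30% | 0.0124/0.39 = 3.18% | 4.84% |
| Afebrile testing stopped: 0/50/80% | 0.0269/0.3328 = 8.08% | 0.0440/0.64 = 6.88% | 7.09% |
| High-suspicion testing up: 15/50/95% | 0.0314/0.4186 = 7.51% | 0.0284/0.55 = 5.16% | 5.98% |

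The third row is the clearest. The negative percentage rises by about one point although the share of children treated without a positive test does not rise. In the second row the all-children measure falls because fewer children are actually treated without a positive test. That is a real effect of the intervention, reached through testing, and randomisation supports it.

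**Meaning of untested.** If only febrile untested children count, the reference value is (0.20×0.10 + 0.04×0.50)/0.24 = 16.7%. Raising low-suspicion testing from 50% to 95% gives (0.02×0.10 + 0.04×0.50)/0.06 = 36.7%, a large shift against ePOCT+. Under the second row's testing it is (0.04×0.10 + 0.01×0.50)/0.05 = 18.0%.

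**Sensitivity.** A grid of 104,976 combinations varied the shares, the untested and negative prescribing rates, and testing in both arms (assumed ePOCT+ febrile testing 85–95%, assumed control 40–60% in low and 70–85% in high suspicion). The negative percentage moved by −4.2 to +4.2 points and rose in 45% of combinations. The untested percentage over all children moved by −15.9 to +2.8 points and rose in 2%. These shares describe the grid; they are not probabilities.

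**When nothing moves.** With u = 10% and n = 5% for every child type, the percentages stay at 10.0% and 5.0% whatever the testing.

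**The case against.** The strongest reply is that the premise is not quantified. Table 2 says that the malaria test is routinely available at this level of care and is not project-supplied. Section 8.1.6 gives control staff the IMCI and national guidelines with a reminder to follow them, and lets intervention staff override the tool. Testing may therefore differ little between arms, and then little moves. This stands as a limit on size. It does not remove the mechanism, since the protocol itself lists testing as an outcome to be compared.

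A second reply is that testing coverage heads the same list, so the four outcomes form a cascade to be read together. That helps a reader, but it does not turn the later steps into randomised comparisons. An outcome defined on a subset does not by itself breach 10.3's intention-to-treat statement; the difficulty is that the intervention can shape this subset.

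A third reply is that 10.3 addresses the primary outcomes and defers detail to a statistical analysis plan. The Phase 1 SAP is not supplied, so handling there cannot be excluded.

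A reader might infer something stronger: that the untested outcome will falsely worsen under ePOCT+ while the negative outcome falsely improves. Under an all-children reading the documents do not support this. Take a population of febrile children only, 30% high suspicion, with untested children treated 60% (high) and 5% (low). If testing goes from 70%/20% to 95%/95%, the untested percentage rises from 12.6% to 21.5%. But 5.1 enrols any acute medical or surgical problem, and Table 2 targets the malaria test at fever. Let 5% of children be afebrile, 5% of them tested in both arms and 1% treated if untested, and the change is 11.8% to 11.3%; at 20% afebrile it is 9.5% to 4.6%.

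**Conclusion.** The point holds as a structural weakness in secondary outcomes. Antimalarial prescribing is compared between arms only within groups that form after randomisation and that the intervention can reshape. A distortion needs two conditions: a between-arm difference in who is tested, and prescribing that varies among the children who change group. The documents quantify neither, so the size is unknown.

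Under the assumed rates, the negative percentage can shift either way by about a point (7.0% to 6.3%, or to 8.1%). The untested percentage over all children usually shifts in favour of ePOCT+ (7.5% to 3.2%), so the likelier risk there is flattering the intervention. A shift against ePOCT+ arises mainly under a febrile-only reading, which 7.1 neither states nor rules out. The malaria-positive outcome shares the conditional denominator.

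Neither co-primary outcome is affected. The supplied SAP is a weaker case: the outcomes there are exploratory and both arms use ePOCT+, so any reshaping would have to come from medAL-mentor. The point applies mainly to the protocol.

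**What to change.** In 7.1 and 10.3:

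1. Add, as the between-arm antimalarial comparison, the percentage of all enrolled children prescribed an antimalarial without a positive malaria test. It can be repeated among all febrile children.
2. State whether untested means all untested children or only febrile ones.
3. Keep the percentages within positive, negative and untested children. Report them beside the testing proportion, and say that they are conditional on testing and are not randomised effects.

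The outcome among malaria-positive children should not be replaced by a share of all enrolled children who test positive and are treated. That share rises with testing alone: in the model above, test-positives go from 0.0006 + 0.0080 + 0.0192 = 2.78% of children to 0.0006 + 0.0144 + 0.0228 = 3.78% when febrile testing goes up. The existing outcome answers a question that the rationale raises directly, whether children with a positive test receive treatment.

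The cost is a few lines of wording and one extra model. Sections 8.1.2 and 8.1.7 already have tests, results and treatments recorded in both arms. If the Phase 1 SAP already covers this, a cross-reference in 10.3 is enough.

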- Primary referral is a decision of referring the child to hospital taken by the HCW at the initial consultation - Secondary referral is a decision of referring the child to hospital taken by the HCW during a re-attendance visit taking place from the day after initial consultation up to day 7 included.
- Primary hospitalization is an admission to a hospital ward taking place the same day as the initial consultation
- Secondary hospitalization is an admission to a hospital ward taking place from the day after initial consultation up to the phone call at day 7 included. A non-referred secondary hospitalization is a direct visit to hospital without a re-attendance visit the same day at a HF participating in the study.
- Antibiotic prescription is any oral, intramuscular or intravenous (but not topical) antibiotic prescribed by a HCW during the initial consultation or a re-attendance visit
- Antimalarial prescription is any oral, rectal, intramuscular or intravenous antimalarial prescribed by a HCW during the initial consultation or a re-attendance visit
- Febrile child is a child with a history of fever and/or a high temperature
- Malaria testing is a malaria RDT or microscopy ordered by a HCW during an outpatient visit
- Day 7 is a range of 6-14 days post initial consultation to allow for completion of home visit for children whose caregiver reports having no phone / no phone number.

Additional longitudinal analyses:

- Change in % of children prescribed an antibiotic over time
- Change in % of children with basic anthropometrics and clinical signs measured over time (intervention arm only)
- Change in % of consultations where ePOCT+ was used over time (intervention arm only)

7.2 Indicators for Objective 2: Improve the algorithm and adapt it to spatiotemporal variations

- Number of positive impact modifications in the algorithm identified by ML-based analyses
- Number of positive impact modifications tested through randomized sub-studies
- % of these positive impact modifications confirmed to be safe and useful by randomized sub-studies
- Number of modifications implemented by type of impact (better clinical cure, less severe clinical outcomes, less medicines or diagnostic tests needed, shorter consultation time...)

Definitions used for the indicators of objective 2

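### A non-referred secondary hospitalization is defined by the lack of a same-day facility visit, not by the lack of a referral, so the Phase 1 co-primary cure endpoint misclassifies some children

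*Protocol*

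**What the plan says.** The definitions are in Protocol section 7.1.

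- Timing splits admissions into two kinds. "Primary hospitalization is an admission to a hospital ward taking place the same day as the initial consultation". Anything later is secondary: "Secondary hospitalization is an admission to a hospital ward taking place from the day after initial consultation up to the phone call at day 7".
- The qualifier non-referred is then given its own rule: "A non-referred secondary hospitalization is a direct visit to hospital without a re-attendance visit the same day at a HF participating in the study".
- A re-attendance visit can occur only from the day after the initial consultation, and it may be at a facility outside the study.
- Referral is defined separately, in the same list. "Primary referral is a decision of referring the child to hospital taken by the HCW at the initial consultation"; a secondary referral is the same decision taken at a re-attendance. The rule for non-referred uses neither definition.
- The link to the endpoint is explicit: "Non-referred secondary hospitalizations (see definition below) will however be considered as clinical failures even if the child is already cured at day 7". The synopsis repeats this link without defining the term.
- Non-referred secondary hospitalization is also a secondary outcome under severe outcomes. A further secondary outcome is the percentage "of children who were hospitalized among those referred (i.e. referral completed"), which carries no same-day limit.

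Sections 10.1.1 and 10.3 make the antibiotic comparison conditional on non-inferiority of clinical cure. The supplied SAP covers the medAL-mentor study and does not define this endpoint.

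**The concern.** The label says that no referral was made; the rule asks whether a participating facility saw the child on the day of admission. These are different questions, and the answer decides whether a recovered child counts as a cure or a failure.

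The endpoint is rare (3% assumed failure) and the margin is narrow (0.9 points at that rate), so a small misclassified group matters. Referral is also something the tool acts on: it is the first item on which ePOCT+ guides clinicians (section 6.1), and section 1.7 expects better identification of children who need it. Next-day admission is plausible, because children are enrolled after working hours as well (section 8.1.1), the initial-consultation window closes at midnight (section 7.1) and the sites are rural and semi-urban (section 4.1). Because the cure test gates the antibiotic test, one definition affects both co-primary outcomes.

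**Working it through.** **Step 1. Apply the rule to five paths.** Each child is reported cured or improved at the day 7 call. HF means a participating facility.

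| Path | Referred? | HF re-attendance on admission day? | Label under the rule | Score |
|---|---|---|---|---|
| A. Referred day 0, admitted day 1 | Yes | No | Non-referred | Failure, and also a completed referral |
| B. Referred at re-attendance day 3, admitted day 4 | Yes | No | Non-referred | Failure |
| C. Re-attends day 3, not referred, admitted day 3 | No | Yes | Not non-referred | Cure |
| D. Referred at re-attendance day 3, admitted day 3 | Yes | Yes | Not non-referred | Cure |
| E. Never referred, no re-attendance, admitted day 3 | No | No | Non-referred | Failure |

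Label and rule agree only in D and E. In A, the visit that produced the referral can never satisfy the rule, because a re-attendance cannot fall on day 0. A child sent to hospital the same day by a facility outside the study is also labelled non-referred. This step needs no assumption.

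**Step 2. Reproduce the plan's sample size, to obtain the design effect.** Inputs (section 10.1.1): failure 3%, margin 0.9 points, one-sided alpha 0.025, power 80%, cluster size 900, ICC 0.002.

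- Per arm, unclustered: (1.960 + 0.842)² × 2 × 0.03 × 0.97 / 0.009² = 5,640.
- Design effect: 1 + 899 × 0.002 = 2.798.
- 5,640 × 2.798 = 15,781; divided by 900 = 17.53 clusters. Adding one cluster per arm gives 18.53, rounded up to 19, or 17,100 children.
- 34,200 × 1.10 = 37,620. Both stated figures are reproduced.

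**Step 3. Illustrate path A.** The documents give neither the share of children referred on day 0 (r) nor the share of those admitted from day 1 who would otherwise count as cured (d). Both are assumptions: r from 1% to 5%, d from 10% to 50%.

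Observed failure = true failure + r × d. The addition runs from 1% × 10% = 0.1 points to 5% × 50% = 2.5 points, or about 17 to 428 children per 17,100.

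Chance of concluding non-inferiority = Φ[(ln 1.3 − ln(pI/pC))/SE − 1.960], with SE = √(2.798 × [(1−pI)/pI + (1−pC)/pC] / 17,100). Here pI and pC are the observed failure proportions under ePOCT+ and control.

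| True RR | r control / ePOCT+ | d | Observed failure, control / ePOCT+ | Observed RR | Chance of concluding NI |
|---|---|---|---|---|---|
| 1.0 | none | – | 3.0% / 3.0% | 1.00 | 0.72 |
| 1.0 | 1% / 2% | 10% | 3.1% / 3.2% | 1.03 | 0.63 |
| 1.0 | 1% / 2% | 30% | 3.3% / 3.6% | 1.09 | 0.45 |
| 1.0 | 1% / 2% | 50% | 3.5% / 4.0% | 1.14 | 0.29 |
| 1.0 | 2% / 4% | 30% | 3.6% / 4.2% | 1.17 | 0.22 |
| 1.0 | 2% / 1% | 30% | 3.6% / 3.3% | 0.92 | 0.95 |
| 1.0 | 2% / 2% | 30% | 3.6% / 3.6% | 1.00 | 0.80 |
| 1.3 | none | – | 3.0% / 3.9% | 1.30 | 0.025 |
| 1.3 | 1% / 1% | 10% | 3.1% / 4.0% | 1.29 | 0.03 |
| 1.3 | 2% / 2% | 30% | 3.6% / 4.5% | 1.25 | 0.065 |
| 1.3 | 5% / 5% | 50% | 5.5% / 6.4% | 1.16 | 0.34 |
| 1.3 | 2% / 1% | 30% | 3.6% / 4.2% | 1.17 | 0.22 |

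The baseline is 0.72 rather than 0.80 because this calculation uses the log risk ratio, whereas the plan's 19 clusters reproduce on the risk-difference scale. That is a separate matter. As a yardstick, 0.9% of 17,100 is about 154: that many such children under ePOCT+ and none in control would move a true ratio of 1.0 to 1.3.

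Paths B and C are not quantified. C works the other way, removing failures.

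**The case against.** A reader might infer that the rule biases the trial against ePOCT+. The documents do not support that. They give no referral rate or admission delay by arm, and better identification of children who need referral does not mean more referrals; sharper targeting could leave the total unchanged or lower it. The risk ratios above 1 depend on invented referral rates and on treating every late admission as otherwise cured. If half of those children failed anyway, the 2% v 4% row falls from 1.17 to (3 + 0.6)/(3 + 0.3) = 1.09. Children admitted to a health-centre ward at the initial consultation also count among primary referrals and cannot be late. All of this stands.

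It can also be said that a direct visit to hospital implies that nobody sent the child, so the wording is only loose. That does not rescue the rule: the sentence specifies the visit by the lack of a same-day re-attendance and does not mention referral, so two programmers could code it differently. A separate Phase 1 SAP, mentioned in SAP section 5.2.1, may settle the matter, but it was not supplied.

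One child may properly enter both a process measure and a clinical outcome, so the double count is not a contradiction in itself. The oddity is that the child is non-referred in one and referred in the other.

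Finally, exempting every admission after a day 0 referral would hide a child whose referral was not taken up and who deteriorated days later, and could shield the arm that refers more. This objection is sound and shapes the fix.

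**Conclusion.** The defect is established from the text alone. The rule does not measure what its name says, and read literally it misclassifies children in both directions on a gating co-primary endpoint and on the severe-outcome secondary endpoint.

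The effect on the between-arm comparison cannot be derived from the documents. If referral or delay differs by arm, the bias can go either way. If they are equal, a true ratio of 1 is unchanged, but a true ratio of 1.3 is diluted: to between 1.29 and 1.16 over the assumed ranges, with the chance of wrongly concluding non-inferiority rising from 0.025 to between 0.03 and 0.34. These figures are illustrations that assume 3% true control failure, independent additive misclassification from path A only, and the planned 19 clusters of 900 per arm.

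**What to change.** 1. Define a secondary hospitalization as non-referred when no referral decision was recorded at the initial consultation or at any re-attendance at a participating facility before the admission. Apply this to Phase 1 and to the matching Phase 2 indicator.
2. State how the definition fits with the completed-referral outcome, so that a child admitted after a day 0 referral is treated as referred in both.
3. Report the cure endpoint in two further versions: under the present same-day rule, and under a rule that exempts a referred child only if admission follows the referral within a short prespecified interval. The second version keeps late deterioration after a referral not taken up visible as failure.
4. Since SAP section 2.1 already cites preliminary Phase 1 findings, date the change and show all three results together.

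The cost is one reworded definition, one derivation and two extra analyses. Referral decisions are entered on the tablets in both arms (sections 8.1.2 and 8.1.7), visits can be linked across participating facilities (section 8.1.3), and the present definition already needs the admission date. The remaining weakness is that consultations at facilities outside the study leave no data (section 8.1.3), so children referred from there stay classed as non-referred. The report should say so.
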